3.6 SELECTION OF STUDY POPULATION

3.6.1 Inclusion Criteria

Eligible subjects will be considered for inclusion in this study if they meet all the following criteria:

- 1. CLL diagnosed according to IWCLL criteria within one year prior to randomization
- 2. High risk of infection and/or progressive treatment within 2 years according to CLL-TIM
- 3. IWCLL treatment indication not fulfilled
- 4. Life expectancy > 2 years
- 5. Age at least 18 years
- 6. Ability and willingness to provide written informed consent and adhere to study procedures and treatment
- 7. Adequate bone marrow function as indicated by platelets above 100 x 10E9, hemoglobin above 10 g/dL and neutrophils above 1 x 10E9
- 8. Creatinine clearance above 30 mL/min directly measured with 24hr urine collection or calculated according to the modified formula of Cockcroft and Gault
- 9. Adequate liver function as indicated by a total bilirubin≤ 2 x, AST or ALT ≤ 2.5 x the institutional ULN value, unless directly attributable to the patient's CLL or to Gilbert's Syndrome.
- 10. Negative serological testing for hepatitis B (HBsAg negative and anti-HBc negative; patients positive for anti-HBc may be included if PCR for HBV DNA is negative and HBV-DNA PCR is performed every month until 12 months after last treatment cycle), negative testing for hepatitis C RNA within 6 weeks prior to registration.
- 11. Eastern Cooperative Oncology Group Performance Status (ECOG) performance status 0-2.
- 12. Woman of childbearing potential (WOCBP) who are sexually active must use highly effective methods of contraception during treatment and for 30 days after the last dose of investigational drugs.
- 13. Willing and able to participate in all required evaluations and procedures in this study protocol including swallowing capsules without difficulty.
- 14. Ability to understand the purpose and risks of the study and provide signed and dated informed consent and authorization to use protected health information.

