3.10.2 Dosing Delays and Modification for Venetoclax

Dose modification for TLS and other toxicities.

Dose at interruption (mg)	Restart dose (mg ^a)
400	300
300	200
200	100
100	50
50	20
20	10
aThe modified dose should	

before increasing the dose.

For patients who have had a dosing interruption lasting more than 1 week during the first 5 weeks of dose titration or more than 2 weeks after completing the dose-titration phase, TLS risk should be reassessed to determine if restarting at a reduced dose is necessary (e.g., all or some levels of the dose titration).

Venetoclax Recommended Dose Modifications for Toxicities

Event	Occurrence	Action				
Tumor Lysis Syndrome						
Blood chemistry changes or symptoms suggestive of TLS (Cairo-Bishop grading in Appendix 6)	Any	Withhold the next day's dose. If resolved within 24-48 hours of last dose, resume at the same dose.				
		For any blood chemistry changes requiring more than 48 hours to resolve, resume at one dose level reduction				
		For any events of clinical TLS, resume at one dose level reduction following resolution				
Non-Hematologic Toxicit	ties					
Grade 3 or 4 non- hematologic toxicities	1 st occurrence	Interrupt venetoclax Once the toxicity has resolved to Grade 1 or baseline level, venetoclax therapy may be				

Event	Occurrence	Action				
		resumed at the same dose. No dose modification is required.				
	2 nd and subsequent occurrences	Interrupt venetoclax. Restart at one dose level reduction when resuming treatment with venetoclax after resolution. A larger dose reduction may occur the discretion of the investigator.				
Hematologic Toxicities						
Grade 3 or 4 neutropenia with infection or fever; or Grade 4 hematologic toxicities (except lymphopenia)	1 st occurrence	Interrupt venetoclax. To reduce the infection risks associated with neutropenia, granulocyte-colony stimulating factor (G-CSF) may be administered with venetoclax if clinically indicated. Once the toxicity has resolved to Grade 1 or baseline level, venetoclax therapy may be resumed at the same dose.				
	2 nd and subsequent occurrence	Interrupt venetoclax. Consider using G-CSF as clinically indicated. Restart at one dose level reduction when resuming treatment with venetoclax after resolution. Additional dose reductions may occu at the discretion of the physician. Re-escalation on the discretion of the treating physician				

Patients who require dose reductions to less than 100 mg for more than 4 weeks should stop treatment.

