Management of Neutropenia

Nonclinical and clinical experience indicates that venetoclax may cause neutropenia. Subjects with a history of neutropenia or with significant bone marrow involvement may be at a particularly high risk.

Grade 3 or 4 neutropenia has been reported in patients treated with venetoclax. Complete blood counts should be monitored throughout the treatment period. Dose interruptions or dose reductions are recommended for patients with severe neutropenia. Supportive measures including antimicrobials for any signs of infection should be considered and prophylactic use of growth factors (e.g. G-CSF) is mandatory for patients with neutrophil counts below 1x10⁹/L.

Management of Hematologic Toxicities Other Than Neutropenia or Lymphopenia

Venetoclax treatment should be withheld for any Grade 4 hematologic toxicity. Once the toxicity has resolved to Grade 1 or baseline level (recovery), venetoclax may be re-started at the same dose administered prior to holding the drug. If the toxicity recurs, the dose reduction guidelines in

table I1 should be followed when resuming study treatment following resolution. Additional dose reductions may occur at the discretion of the physician.

Management of Non-Hematologic Toxicity

Venetoclax treatment should be withheld for any clinically relevant ≥ Grade 3 non-hematologic toxicity. Once the toxicity has resolved to Grade 1 or baseline level (recovery), venetoclax may be re-started at the same dose administered prior to holding the drug. If the toxicity recurs, the dose reduction guidelines in table I1 should be followed when resuming study treatment following resolution. Additional dose reductions may occur at the discretion of the physician.

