4.1.13 Hepatitis B and C Testing

Hepatitis serology testing must include hepatitis B surface antigen (HBsAg), hepatitis B surface antibody (anti-HBs), anti-HBc, and HCV antibody. In addition, any subjects testing positive for any hepatitis serology must have monthly PCR testing during screening and on treatment, thereafter 3-monthly PCR for the next year.

Subjects who are anti-HBc positive should have quantitative PCR testing for HBV DNA performed during screening and monthly thereafter as per institutional practices. Any subject with a rising viral load (above lower limit of detection) should discontinue study drug and have antiviral therapy instituted and a consultation with a physician with expertise in managing hepatitis B. As IVIG may cause false positive hepatitis serology, monthly PCR testing is not required in subjects who are currently receiving or received prophylactic IVIG within 3 months before study enrollment and have a documented negative anti-HBc test before the initiation of IVIG therapy. PCR testing should be performed when clinically indicated (e.g., in the setting of rising transaminase levels).

Subjects with a known history of hepatitis C or who are hepatitis C antibody positive should be excluded from study.

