Pregnancy test ⁵		Х	X ⁶				X ⁷	X ⁷	X ⁷					
ECOG Performance	X	Χ												
ECG		Х												
(PET)-CT scan		Х								Χ				Χ
Lab tests														
Hematology		Х	Х	Х	Χ	X	Χ	Χ	X	Χ		X	Х	Χ
Blood chemistry		Х	X	Х	Χ	Χ	Χ	Χ	X	Χ		X	X	Х
Additional chemistry		Х								Х		X	X	Х
Virology		Х								Х		Х	Х	Χ

¹ No laboratory testing except for standard of care based on the discretion of the local investigator, this visit is for informed consent to assemble data for assessment by the CLL-TIM algorithm

² Max 42 days from screening to randomization, however FISH and TP53 mutational results are accepted up to six months prior to randomization, max 14 days from randomization to cycle 1 day 1 (C1D1)

³ Only for treatment arm.

⁴ TLŚ chemistry the day before, 6 h after ramp up dose of venetoclax and the day after (24 h) before next dose of venetoclax

⁵ Only applies for women of child bearing potential

⁶ A negative pregnancy test is required for all women of child bearing potential within 7 days before start of study treatment

⁷ Only applies for the women of child bearing potential in the treatment arm

Biobank blood	Х	X ³	X ³	Χ	Х	Х	Χ	Х	Х	Χ
Central lab										
IGHV, FISH, Recur	Χ									Х
Flow-MRD	Χ					Х	Χ	Х	Х	Χ
PK samples					X8					
Bone marrow										
Biopsy and aspirate	Х			Χ	Х	Х	Χ			Χ
Aspirate biobank	Х						Χ			X ⁹
Microbiome samples										
Feces, saliva, skin, buccal swabs	X					Х	Х			

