- Post-dose Monitor clinical chemistries (see under 'laboratory assessments') for evidence of TLS at 6 – 8 hours after the first dose of 20 mg and 50 mg. The 6-8-hour post-dose laboratory values must be reviewed prior to a patient leaving the clinic and electrolyte abnormalities should be corrected promptly
- Serum chemistries must be re-assessed before administering the second dose of each rampup (i.e., at 24 hours).
- Any patient who, at any dose, develops clinically significant electrolyte abnormalities must have his or her subsequent venetoclax dose withheld until the electrolyte abnormalities resolve.
- Patients who develop electrolyte abnormalities should undergo aggressive management and further monitoring as outlined below (see under 'further actions')'.
- Oral hydration consisting of fluid intake of >2 L/day should be maintained during the whole ramp-up period of venetoclax.

High risk patients

- Administration of an oral uric acid reducer (such as allopurinol 300 mg/day) beginning at least 24 hours prior to first dose and continued until at least 28 days after last dose escalation.
- Laboratory assessment of clinical chemistries (see under 'laboratory monitoring') and assessment of vital signs are required pre-dose, 6-8 and 24 hours post-dose on the first day of each dose level, The pre-dose laboratory samples are to be reviewed prior to dosing and should not demonstrate any clinically significant abnormalities prior to the first dose of venetoclax, or the patient should receive additional prophylactic treatment and hydration prior to the initiation of dosing.
- Post-dose: Monitor clinical chemistries (see under 'laboratory assessments') for evidence of TLS at 6 – 8 hours at first dose of each dose level. The 6-8-hour post-dose laboratory values must be reviewed prior to a patient leaving the clinic and electrolyte abnormalities should be corrected promptly
- Serum chemistries must be re-assessed before administering the second dose of each rampup (i.e., at 24 hours).
- Any patient who, at any dose, develops clinically significant electrolyte abnormalities must have his or her subsequent venetoclax dose withheld until the electrolyte abnormalities resolve.
- Patients who develop electrolyte abnormalities should undergo aggressive management and further monitoring as outlined below (see under 'further actions')'.
- Oral hydration consisting of fluid intake of >2 L/day should be maintained during the whole ramp-up period of venetoclax.

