The following table summarizes the safety precautions for mitigation of TLS depending on different risk categories:

Recommended TLS Prophylaxis Based on Tumor Burden from Clinical Trial.

Data (consider all patient co-morbidities before final determination of prophylaxis and monitoring schedule).

	Tumor Burden	Proph	nylaxis	Blood Chemistry Monitoring ^{c,d}		
		Hydrationa	Anti- hyperuricemics	Setting and Frequency of Assessments		
Low	All LN <5 cm AND ALC <25 x10 ⁹ /L	Oral (1.5-2 L)	Allopurinol ^b	Outpatient 1. Pre-dose, 6 to 8 hours, 24 hours at first dose of 20 mg and 50 mg 2. Pre-dose and 24 hours at at subsequent ramp- up doses		
Medium	Any LN 5 cm to <10 cm OR ALC ≥25 x10 ⁹ /L	Oral (1.5-2 L) and consider additional intravenous	Allopurinol	Outpatient 3. Pre-dose, 6 to 8 hours, 24 hours at first dose of 20 mg and 50 mg 4. Pre-dose and 24 hours at subsequent ramp-up doses 5. Consider hospitalization for subjects with CrCl <80mL/min at first dose of 20 mg and 50 mg; see below for monitoring in hospital		
High	Any LN ≥10 cm OR ALC ≥25 x10 ⁹ /L AND any LN ≥5 cm	Oral (1.5-2 L) and intravenous (150-200 mL/hr as tolerated)	Allopurinol; rasburicase is recommended if baseline uric acid is elevated (ALLOPURINOL SHOULD NOT BE GIVEN AT SAME DAY AS RASBURICASE)	In hospital (recommended) at first dose of 20 mg and 50 mg 6. Pre-dose, 6 to 8, and 24 hours Outpatient at subsequent ramp-up doses 7. Pre-dose, 6 to 8 hours, 24 hours		

ALC = absolute lymphocyte count; LN = lymph node.

- a Administer intravenous hydration for any patient who cannot tolerate oral hydration.
- b Start allopurinol or xanthine oxidase inhibitor at least 1 day prior to initiation of venetoclax.
- c Evaluate blood chemistries (potassium, uric acid, phosphorus, calcium, and creatinine); review in real time
- For subjects at low/medium risk of TLS, monitor blood chemistries pre-dose and 24 hours at each subsequent ramp-up dose. For subjects at high risk of TLS, monitor blood chemistries pre-dose, at 6-8 hours and at 24 hours at each dose level.

Hydration: Ensure adequate hydration prior to initiating therapy with venetoclax and throughout the ramp-up phase, especially the first day of each ramp-up dose. Administer intravenous (IV) fluids as indicated based on overall risk of TLS or for those who cannot maintain adequate oral hydration.

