Anti-hyperuricemic agents: Administer uric acid reducing agents (e.g., allopurinol). Start at least 1 day prior to initiation of venetoclax; consider continuing through the ramp-up phase.

Laboratory Assessments:

Pre-dose (within 24 hours prior to ramp-up dose):

- Sodium, potassium, calcium, phosphate, chloride
- uric acid, urea, total bilirubin, serum creatinine
- LDH
- complete blood count (CBC), including hemoglobin, platelets and white blood cell count with differentials
- liver enzymes (AST, ALT, alkaline phosphatase)

_

Assess blood chemistries mentioned above prior to initiating venetoclax to evaluate kidney function and correct pre-existing hyperuricemia, hyperkalemia, hyperphosphatemia, or hypocalcemia to normal levels. Reassess blood chemistries before starting each subsequent ramp-up dose of venetoclax.

Post-dose: For subjects at low or medium risk of TLS, monitor blood chemistries at 6-8 hours and at 24 hours after initiating venetoclax at the 20 mg and 50 mg doses. For subjects at high risk of TLS, monitor blood chemistries in the hospital at 4, 8, 12 and 24 hours after initiating venetoclax at the 20 mg and 50 mg doses; subsequent ramp-up doses can be administered in the outpatient setting with monitoring of blood chemistries at 6-8 hours and at 24 hours after initiating venetoclax. Electrolyte abnormalities should be corrected promptly. The next dose of venetoclax should not be administered until the 24-hour blood chemistry results have been evaluated.

Hospitalization:

Based on physician assessment, some patients, especially those at greater risk of TLS, may require hospitalization on the day of the first dose of venetoclax for more intensive prophylaxis and monitoring during the first 24 hours. Hospitalization should be considered for subsequent dose increases based on reassessment of risk.

Scoring of tumor lysis syndrome and further actions

The below listed criteria defined by Cairo and Bishop should be used to diagnose a laboratory or clinical TLS.

Laboratory Tumor Lysis Syndrome (LTLS):

Laboratory Parameter	Laboratory Result
Uric Acid	≥ 476 µmol/L (≥ 8.0 mg/dL) or 25% increase from baseline
Potassium	≥ 6.0 mmol/L (≥ 6.0 mEq/L) or 25% increase from baseline
Phosphorous	≥1.45 mmol/L (≥ 4.5 mg/dL) or 25 % increase from baseline
Calcium	≤ 1.75 mmol/L (≤ 7.0 mg/dL) or 25% decrease from baseline

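### Instructions on tumor lysis sampling for high-risk patients, growth factor use, hepatitis B PCR and hepatitis C eligibility contradict each other and must be reconciled

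*Protocol*

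**What the plan says.** **TLS sampling, high-risk patients, 20 and 50 mg.** Under Laboratory Assessments, Appendix 6 says to "monitor blood chemistries in the hospital at 4, 8, 12 and 24 hours after initiating venetoclax at the 20 mg and 50 mg doses". The bullets for high-risk patients say chemistries and vital signs are "required pre-dose, 6-8 and 24 hours post-dose on the first day of each dose level". The table footnote says: "For subjects at high risk of TLS, monitor blood chemistries pre-dose, at 6-8 hours and at 24 hours at each dose level". The setting differs too. The laboratory text takes a hospital stay as given, the table only recommends it, and the Hospitalization paragraph leaves it to the physician.

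**Growth factor.** In section 3.10.2 the neutropenia paragraph says "prophylactic use of growth factors (e.g. G-CSF) is mandatory for patients with neutrophil counts below" 1x10⁹/L. The toxicity table in the same section says "granulocyte-colony stimulating factor (G-CSF) may be administered with venetoclax if clinically indicated" at a first occurrence, and asks only that it be considered at later ones. Section 3.10.1 (acalabrutinib) describes growth factors as permitted.

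**Hepatitis B.** Inclusion criterion 10 (synopsis and 3.6.1) admits anti-HBc-positive patients with negative HBV DNA if PCR is done "every month until 12 months after last treatment cycle". Section 4.1.13 first sets monthly PCR at screening and on treatment for anyone with positive hepatitis serology, "thereafter 3-monthly PCR for the next year". Its next paragraph asks for monthly PCR in anti-HBc-positive patients in line with local practice, with no end date.

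**Hepatitis C.** Criterion 10 requires a negative RNA test. Section 4.1.13 says that patients with a history of hepatitis C or a positive antibody should be excluded.

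**The concern.** Each conflict concerns a harm that the protocol itself reports: fatal TLS (1.6.3.1), fatal sepsis alongside neutropenia (1.6.3.2) and a fatal hepatitis B reactivation (1.4.2.2). The patients would normally not be treated at all, and about 7 centers in three countries will each read the text for themselves. For the patients concerned, sampling, supportive care and, for hepatitis C, eligibility would depend on the page that a site follows.

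The growth factor conflict also touches the analysis. The phase 2 primary endpoint is grade ≥3-infection-free survival at 24 weeks with 25 patients per arm. The toxicity table gives reducing infection risk as the reason for G-CSF. Use that varies by site would therefore add variation to the treatment-arm event rate that the protocol does not control.

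**Working it through.** The check is a comparison of the instructions for one and the same patient, with simple counts. The protocol states no figure of its own here to reproduce.

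**1. TLS, high risk, 20 and 50 mg**

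| Source in Appendix 6 | Post-dose draws | Per dose | Two doses |
|---|---|---|---|
| Laboratory Assessments, post-dose text | 4, 8, 12, 24 h | 4 | 4 × 2 = 8 |
| High-risk bullets, table, table footnote | 6-8, 24 h | 2 | 2 × 2 = 4 |

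The 8 h draw falls in the 6-8 h window and both schedules include 24 h, so a site following the laboratory text also meets the others. The reverse fails, because the 4 h and 12 h draws are omitted. A cross-reference to in-hospital monitoring stands only in the medium-risk row of the table. The high-risk in-hospital row itself states 6-8 and 24 h. The group is not empty by design: Appendix 6 handles creatinine clearance of 30-50 mL/min as high risk, and inclusion criterion 8 admits clearance above 30 mL/min.

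**2. Growth factor**

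The table row covers grade 3-4 neutropenia with infection or fever, and grade 4 hematologic toxicity. Section 3.10.1 gives grade 4 neutropenia as below 500/µL, that is 0.5x10⁹/L. Every grade 4 case is therefore also below the 1x10⁹/L threshold and falls under both instructions. Grade 3 cases with infection or fever do so as well where the count is below the threshold. Uncomplicated grade 3 neutropenia is outside the table row, so that patient meets only the compulsory rule within 3.10.2.

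Size, using the venetoclax-rituximab rates in 1.6.3.2 and 25 treated patients:
- grade 4: 0.26 × 25 = 6.5
- febrile neutropenia: 0.04 × 25 = 1.0
- overlap: 6.5 if all febrile cases are already grade 4, and 6.5 + 1.0 = 7.5 if none is. That is roughly 7 of 25.

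The 4% stands in for grade 3 with infection or fever. The protocol gives no rate for that group as such.

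**3. HBV DNA PCR, anti-HBc positive, 12 months after treatment**
- Inclusion criterion 10: monthly, 12 tests.
- 4.1.13, first paragraph: 3-monthly, 12 / 3 = 4 tests.
- 4.1.13, second paragraph: monthly, no end stated, so no fixed number.

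**4. Hepatitis C**

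Take a patient who is antibody positive and RNA negative. Criterion 10 is met. No hepatitis criterion appears in 3.6.2. Section 4.1.13 says to exclude. The two sections give opposite answers on eligibility.

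**The case against.** Several points on the other side are fair.

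- The laboratory text and the table can be met together by taking the denser schedule. The table is headed as recommended and tells sites to weigh co-morbidities first. The protocol expects lower tumor burden than in other trials, so few patients may be high risk. In the two monotherapy studies with the five-week titration, TLS was 2% and all laboratory. This limits the reach. It does not make the sections agree, and reduced renal function alone puts a patient in the high-risk group.
- Optional wording on growth factor does not forbid what another paragraph requires, and one paragraph speaks of prophylaxis. Both can be followed. But a site working from the table could withhold G-CSF in grade 4 neutropenia and so breach the neutropenia paragraph.
- On hepatitis B, the paragraph of 4.1.13 specific to anti-HBc-positive patients matches the monthly frequency of criterion 10. That stands, so 12 against 4 tests is the extreme reading. The general sentence still covers these patients literally, and the specific one gives no stopping point.

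Stronger readings are tempting but not supported:

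- A reader might add grade 3 (32%) to grade 4 (26%) and get 0.58 × 25 = 14.5 patients under conflicting G-CSF rules. That counts uncomplicated grade 3 neutropenia, which the table row does not cover.
- A reader might also infer that Appendix 1 footnote 4 ("the day before, 6 h after ramp up dose of venetoclax and the day after (24 h) before next dose of venetoclax") contradicts Appendix 6 for low- and medium-risk patients above 50 mg, where Appendix 6 drops the 6-8 h draw. In the available text the marker for footnote 4 sits only on C1D8. That is the 50 mg step, where Appendix 6 also asks these patients for a 6-8 h draw. The markers on C1D15 and C1D22 look garbled: as printed they point to a note ruling out study laboratory tests at visits where such tests are ticked. This supports a question to the sponsor and no more.

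**Conclusion.** The protocol is inconsistent in four places as it stands. The TLS conflict is confined to high-risk patients at 20 and 50 mg: 2 against 4 post-dose draws per dose, and three different statements on hospital stay. The hepatitis C conflict is a direct contradiction on eligibility. The growth factor conflict covers grade 4 neutropenia plus grade 3 with infection or fever below the threshold. Roughly 7 of 25 treated patients rests on the assumption that the cited rates carry over. They probably do not carry over exactly, because that study enrolled previously treated patients, added rituximab and gave venetoclax for 24 months rather than three 28-day cycles. The hepatitis B conflict is one of frequency and duration, and affects only enrolled anti-HBc-positive patients.

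A reader might infer that every treated patient would be monitored differently by site, or that the primary comparison is biased. The documents support neither. The affected groups are limited, and any effect of varying G-CSF use on the infection endpoint is plausible but cannot be sized from the protocol.

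**What to change.** Reconcile the following. The sponsor's clinicians choose each rule, and this review takes no view on which is right.

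- Appendix 6: the high-risk bullets, the table with its footnote, the post-dose laboratory text and the Hospitalization paragraph.
- Section 3.10.2: the neutropenia paragraph and the toxicity table, with the growth factor wording in 3.10.1 checked against the result.
- Inclusion criterion 10 (synopsis and 3.6.1) and both hepatitis B paragraphs of 4.1.13, including a stated end of testing.
- Criterion 10 and 4.1.13 on hepatitis C, so that an antibody-positive, RNA-negative patient gets one answer.

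At the same time, confirm which visits and which TLS risk groups Appendix 1 footnote 4 covers. Send one clarification to all sites. The cost is a clarification letter or amendment wording. Sample size and analysis are untouched.
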